2.1 Potential Studies

The following are described as potential studies and analyses that could be performed from the study materials. They are not specific study hypotheses but show the potential uses for the developing clinical and biologic sample set collected under the study. While individual gene constructs may be mentioned, it should be understood that alternative targets may be identified at later times which might be substituted in the comments that follow. Additional discussion of power or detectable alternatives is included in Section [7](#). Examples of potential studies include:

- **Detecting improved prognostic factors in low risk MDS**

The International Prognostic Scoring System (IPSS) provides a risk-based classification method for patients with MDS. The risk of evolution to AML and overall survival for an MDS patient is associated with their IPSS-risk category [low (33% of unselected MDS patients), INT-1 (38%), INT-2 (22%), and high-risk (7%)]. The current prognostic system cannot distinguish the 19% of low-

risk patients that will die with leukemia from those that will not. The substudy can test whether incorporating the mutational status of single genes can improve the ability to predict who will die with AML in the low-risk group.

- **Detecting markers of improved response to hypomethylating therapy**

Several studies have demonstrated an association between TET2 mutations and an increased likelihood of responding to a hypomethylating agent.

Whether additional mutations influence this association remains unproven.

Out of a cohort of approximately 1750 suspected MDS patients, we anticipate that up to 500 higher risk MDS patients will receive hypomethylating therapy.

Sub group analysis could then be performed for patients with TET2 + other mutations like ASXL1 (occurs in 20%), DNMT3A (occurs in 15%), or one of the frequently mutated splicing factors (cumulatively occur in 50%).

- **QOL and anemia therapy**

Do transfusions improve QOL for MDS patients with moderate anemia? Do erythropoietin stimulating factors? The study can identify transfusion independent individuals with entry hemoglobin within designated limits. Six month changes in QOL scores can be examined in those individuals receiving interventions such as transfusions or erythropoietin.

- **Genetic factors in patients with complex karyotype**

Complex karyotypes, defined as three or more chromosomal abnormalities, have long been associated with increased disease risk and shorter overall survival and are observed in 10% of MDS patients. Recent studies suggest that this association with prognosis might be refined by considering the nature of the chromosomal abnormalities present (e.g., monosomies), the absolute number of abnormalities (e.g., 3 vs. 4. vs 5 or more), or the presence of somatic mutations. Approximately 50% of MDS patients with complex karyotypes will carry a mutation of TP53.

- **Prognostic significance of SF3B1 in MDS patients with Refractory Anemia with Ring Sideroblasts (RARS)**

Among the genes recurrently mutated in MDS, only mutations of SF3B1 have been associated with a longer median survival. Whether this finding is independent of known prognostic features and disease subtypes is unclear.

Rev. Add7

3. Selection of Patients

Rev. 1/17

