7.1 Study Size

As stated in the objectives, this study intends to develop a longitudinal cohort of clinically characterized MDS and ICUS cases with an associated set of biorepository specimens to support multiple basic science, clinical and epidemiologic research studies. As such, a single hypothesis driving a particular statistical comparison does not exist and the selected sample size is instead consistent with pragmatic issues and useful scientific objectives.

Rev. Add7

At the time of study design, it was anticipated that approximately 2000 confirmed MDS cases and 500 ICUS cases would be enrolled based on the eligibility and exclusion criteria in the protocol. Power calculations were performed around these sample size assumptions with the understanding that there were uncertainties in rates of accrual and follow-up as well as in the distribution of disease subgroups. These calculations are retained in Section [7.2](#).

Since designing this study, several factors contributed to reducing the size of the study from what was planned originally. These factors include a slower than anticipated rate of enrollment (gleaned from the vanguard phase that included the first 200 participants), the distribution of disease subgroups of the enrolled participants following central histopathology review, fiscal constraints, and also the unforeseen impact of the COVID-19 pandemic on the study. As a result, it is anticipated that approximately 1750 participants with suspected or newly diagnosed MDS will be enrolled and contribute specimens to the biorepository. Assignment to the disease subgroups and longitudinal or cross-sectional cohorts is being made by the study following centralized review of histopathology, and the available clinical and molecular data. Despite the smaller sample size, it is expected that valuable insights will be gained. As detailed below, with a projected sample size of 500 confirmed MDS cases, the study would have:

- 80% power in detecting a baseline prognostic factor present in 25% of confirmed MDS cases (such as presence of high clonal count subpopulations) that is associated with a minimum 12% decrease in mortality when the 5-year mortality rate is at least 20%.
- Estimated 95% confidence interval widths between 5.3% and 8.8% for event rates (such as progression to AML) that range from 10% to 50%, respectively.

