7.2.1 Comments on Potential Substudies

For each of the potential substudy scenarios identified in Section [2.1](#), additional discussion is provided to describe power and detectable alternatives based on the sample size specified in the original study considerations in Section [7.2](#). When applicable, accrual rate, drop out and study length assumptions are the same as used previously in this section.

- **Detecting new prognostic factors in low risk MDS**

We expect that a study with 2000 MDS cases will have 660 (33% of all MDS patients) low-risk patients. We estimate that these low-risk patients will have a 19% 5 year rate of death with leukemia. For a single low frequency gene (5% mutation rate) the study has 80% power to detect a gene associated with a 45% mortality rate. Additional type 1 error rate adjustment would be required if a set of genes are being explored.

- **Detecting markers of improved response to hypomethylating therapy**

Among 500 higher risk MDS patients who receive hypomethylating therapy, about 250 should respond to treatment while another 250 will show no benefit. Further a TET2 mutation rate of 20% is expected. When the common gene subgroup has a response rate of 45%, we can compute the detectable alternative under a 2 sided 5% level hypothesis test to be 61%. The subgroup with frequently mutated splicing factors has a cumulatively occurrence of 50%. Comparing TET2 mutant patients with a second mutation to TET2 mutant patients without a select second mutation would give 80% power to detect a 25-30% difference in response rate, e.g. 40% versus 67%.

- **QOL and anemia therapy**

The FACT-G has a within person standard deviation of approximately 10. A mean change score difference of 5 approximates that observed in individuals who have temporal changes in performance status class. With this detectable difference 175 individuals equally split between 2 groups provide 90% power.

- **Genetic factors in patients with complex karyotype**

A cohort of 2000 MDS patients will be expected to have 200 with a complex karyotype, 100 of which should carry mutations of TP53. This substudy will have high power to detect large differences in median survival time, e.g. 86% power to detect a difference between median survival times of 2 and 3.8 years.

- **Prognostic significance of SF3B1 in MDS patients with Refractory Anemia with Ring Sideroblasts (RARS)**

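### Section 2.1 expects up to 500 treated higher-risk MDS patients from the current cohort, but the projection in 7.1 implies roughly 145

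*Protocol*

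**What the plan says.** Section 2.1 lists example studies that the resource could support. For the hypomethylating-therapy example it says: "Out of a cohort of approximately 1750 suspected MDS patients, we anticipate that up to 500 higher risk MDS patients will receive hypomethylating therapy". It then proposes subgroup analysis by TET2 plus a second mutation, and its introduction refers the reader to Section 7 for power.

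Under the low-risk example, the same section gives the IPSS distribution as "low (33% of unselected MDS patients), INT-1 (38%), INT-2 (22%), and high-risk (7" (the last figure is 7%).

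Section 7.1 describes the original plan ("it was anticipated that approximately 2000 confirmed MDS cases and 500 ICUS cases would be enrolled") and the reduced one ("it is anticipated that approximately 1750 participants with suspected or newly diagnosed MDS will be enrolled and contribute specimens to the biorepository"). It restates power and precision "with a projected sample size of 500 confirmed MDS cases".

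Section 7.2.1 works out the hypomethylating example: "Among 500 higher risk MDS patients who receive hypomethylating therapy, about 250 should respond to treatment while another 250 will show no benefit". With a TET2 mutation rate of 20%, it gives 61% as the detectable response rate against 45% (two-sided 5%). Among TET2-mutant patients it gives 80% power for 40% versus 67% by second mutation. The opening of 7.2.1 says that its figures use the original sample size.

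**The concern.** The sentence in 2.1 names the current enrolment of about 1750 suspected cases, but its yield equals the whole confirmed MDS cohort projected in 7.1. Both statements can hold only if every confirmed case is higher risk and every one receives hypomethylating therapy. The IPSS split in the same section excludes that, because low risk and INT-1 together make up 71% of MDS patients.

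Section 7.2.1 computes its effect sizes on the same number, 500. A reader who goes from 2.1 to 7.2.1 could therefore conclude that the current cohort supports those effect sizes. Supporting outside investigators is a stated aim of the study (Section 2, aim 3), and 2.1 is where they see what the resource might offer. An overstated subgroup could misinform a proposal.

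**Working it through.** **Inputs**
- Anticipated treated higher-risk patients: up to 500, from about 1750 suspected cases (2.1).
- Projected confirmed MDS, all risk groups: 500 (7.1). Original design: 2000 (7.1, 7.2).
- Higher-risk share: INT-2 22% + high 7% = 29%; low risk 33% (2.1).
- TET2 mutated 20%; splicing-factor mutation 50%; contrasts 45% v 61% and 40% v 67%; two-sided 5% (7.2.1).

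**Step 1: expected counts**
- Original design: 2000 x 0.29 = 580 higher-risk, so 500 treated is coherent (500/580 = 86%).
- Current projection: 500 x 0.29 = 145 if all are treated. At the original treated share, 145 x 500/580 = 125.
- 1750 x 0.29 is about 507, close to the stated 500, but the IPSS shares describe MDS patients and not suspected cases.

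**Step 2: power formula**

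Two independent proportions with pooled null variance:

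power = Φ[(|p1 − p2| − 1.96·s0)/s1]

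Here s0 = √[p̄(1 − p̄)(1/n1 + 1/n2)], s1 = √[p1(1 − p1)/n1 + p2(1 − p2)/n2], and p̄ is the weighted mean rate.

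**Step 3: reproduce 7.2.1 with 500 treated**
- TET2, 400 v 100: p̄ = 0.482, s0 = 0.0559, s1 = 0.0548. Power for 45% v 61% = Φ(0.922) = 82%. The detectable rate at 80% power is 60.6%, which matches the stated 61%.
- Second mutation, 50 v 50: p̄ = 0.535, s0 = 0.0998, s1 = 0.0960. Power for 40% v 67% = Φ(0.776) = 78%, or 80% with unpooled variance. This matches the stated 80%.

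**Step 4: the same contrasts at other sizes**

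| Treated patients | Basis | Power, 45% v 61% | Power, 40% v 67% |
|---|---|---|---|
| 500 | stated in 2.1 and 7.2.1 | 82% | 78% |
| 335 | every patient not low risk, 67% x 500 | 65% | 60% |
| 145 | 29% x 500, all treated | 33% | 30% |
| 125 | 145 x 500/580 | 30% | 26% |

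At 145 the TET2 groups are 116 v 29: s0 = 0.1037, s1 = 0.1017, Φ(−0.426) = 33% (29% by Fisher's exact test). The detectable rate at 80% power becomes 73% against 45%.

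The second-mutation groups are about 14.5 each: s0 = 0.1852, s1 = 0.1783, Φ(−0.522) = 30%. The normal approximation is generous at this size. Fisher's exact test with 15 v 15 gives about 18%.

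**Step 5: size needed for 80% power**
- 45% v 61%: 379 + 95 = 474 treated patients.
- 40% v 67%: 53 per group, so 106 TET2-mutant patients and 106/0.20 = 530 treated.

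**The case against.** Four points can be made for the protocol.

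1. **A reader might take 145 as the most the study can yield.** The documents do not support that. The 29% describes unselected MDS patients, whereas this cohort admits therapy-related disease (3.1), which may form up to 10% of it (7.2.2). Table 1 puts excess-blast disease at 40% of MDS. Taken as a rough proxy for higher risk (an assumption), that gives 500 x 0.40 = 200 patients, with power of 44% and 40%. Section 1.2.1 says that most cases tend to worsen, so more patients could become higher risk during follow-up. This objection stands: 145 is an expectation, and incomplete treatment would lower it. It does not rescue 500, since even 335 falls short for both contrasts.

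2. **A reader might infer that the 7.2.1 figures are wrong.** They are not. Sections 7.1 and 7.2.1 both say that these calculations are retained from the original size, and they reproduce at 500 treated. The problem lies in 2.1, which attaches the same 500 to the current enrolment without such a label.

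3. **The examples are illustrative.** Section 2.1 says that they are not specific hypotheses, and 7.1 says that no single hypothesis set the sample size. No primary analysis depends on the sentence. This limits severity but does not make the count correct.

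4. **A reader might infer that the substudy is impossible, or that a null result would be taken as proof of no marker effect.** Neither follows. Larger differences remain detectable, and the protocol commits to no such analysis or interpretation.

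The wording up to does not resolve the mismatch, because the bound equals the entire confirmed MDS projection.

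**Conclusion.** The count in 2.1 contradicts the projection in 7.1. Under the quoted IPSS shares, roughly 145 treated higher-risk patients would be expected if all were treated, and about 125 at the original treated share, against the 500 stated.

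At 145, power is about 33% for 45% v 61%. For 40% v 67% it is at most about 30%, and about 18% by an exact test. The original figure for both is about 80%.

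The exact count rests on three assumptions: the 500-case projection, the IPSS shares for unselected patients, and complete treatment. The direction does not depend on the case mix, because treating every patient who is not low risk would still give only 65% and 60%. Severity is moderate: an illustrative sentence misstates what the current cohort can offer, and nothing in the study's conduct changes.

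**What to change.** In Section 2.1, do one of the following:
- replace up to 500 with roughly 145 expected, stated as 29% of 500 confirmed MDS and assuming the quoted IPSS shares and that all are treated; or
- keep 500 and label it explicitly as the original-design figure.

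In either case, add a note in 2.1 that the effect sizes in 7.2.1 do not carry over to the current size. At about 145 treated patients, the detectable TET2 response is about 73% against 45%. The second-mutation contrast, with about 15 patients per group, suits only estimation or pooled analysis.

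Section 7.2.1 needs no correction. The cost is a text change in one section, with a less favourable stated figure and no effect on enrolment, procedures or data collection.

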Therefore, the primary objective of the National MDS Study is to establish a longitudinal cohort of up to 1750 participants recently diagnosed with MDS and MDS/MPN overlap disorders. This cohort will provide a standardized clinical dataset linked to a prospectively collected, consistently processed, and well-characterized biospecimen repository that will facilitate the understanding of MDS etiology, pathogenesis and progression; enhance the accuracy of MDS diagnosis, classification, prognosis and survivorship; inform medical decision making for MDS patients; facilitate biomarker discovery; help identify new therapeutic targets as well as define the optimal use of existing therapies; and inform efforts at disease prevention.

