- Direct Antiglobulin Test
- Antinuclear Antibody (ANA) Test
- Creatinine
- Calculated Glomerular filtration rate (GFR)
- Thyroid-Stimulating Hormone (TSH) tests performed in prior 6 months

Rev. Add6

Based on centralized pathology review, participants will be classified into the longitudinal cohort of cases (MDS; MDS/MPN overlap disorders; AML with < 30% blasts without core binding factor or acute promyelocytic leukemia [AML < 30% blasts including chromosomal rearrangements between chromosomes 8 and 21 and within chromosome 16 as well as t(15;17)]; ICUS, or at-risk based on selected genetic markers (described in Section 5.1) of the protocol) and the cross-sectional cohort (all others). It is not known in advance what percentages of individuals will fall into each cohort. In addition to baseline biological samples, longitudinal samples and data will be collected for approximately 1000 participants assigned to the longitudinal cohort. Sample and data collection will cease at baseline for all cases assigned to the cross-sectional cohort. Submitted samples will be reviewed by a central pathologist to determine eligibility for the longitudinal cohort (i.e., an MDS, MDS/MPN, AML with < 30% blasts without core binding factor or acute promyelocytic leukemia, or ICUS diagnosis). Should a discrepancy in diagnosis occur between the central review and study site, the study site will be notified to allow for additional information to be submitted to clarify the diagnosis. Such notifications will not occur in real time, and are not intended to assist in patient care. Additional central sequencing of selected genetic targets will be performed.

Re-screening Subjects

Subjects that are not entered in the longitudinal study are eligible to be re-screened for participation in this study if progression of signs or symptoms provides evidence to support a probable diagnosis of MDS, MDS/MPN overlap disorders or ICUS.

Rev. 1/17
Rev. Add4
Rev. Add5

4. Registration Procedures

CTEP Registration Procedures

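### Section 2.1 expects up to 500 higher-risk MDS patients on hypomethylating therapy from the current cohort, but Section 7.1 now projects only 500 confirmed MDS cases of all risk levels

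*Protocol*

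**What the plan says.** Section 2.1, in the example on response to hypomethylating agents (HMA), says of the current cohort of about 1750 suspected cases: "we anticipate that up to 500 higher risk MDS patients will receive hypomethylating therapy". The same section gives the IPSS risk mix as "low (33% of unselected MDS patients), INT-1 (38%), INT-2 (22%), and high-risk (7" per cent), and refers the reader to Section 7 for power and detectable alternatives.

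Section 7.1 explains that the design-time expectation was that "approximately 2000 confirmed MDS cases and 500 ICUS cases would be enrolled", that the study has since been reduced, and that it now works "with a projected sample size of 500 confirmed MDS cases". It says that the original calculations are kept in Section 7.2.

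Section 7.2.1 states that its substudy figures rest on the original sample size. Its HMA example begins: "Among 500 higher risk MDS patients who receive hypomethylating therapy, about 250 should respond to treatment". It takes a TET2 mutation rate of 20% and a 45% response rate in the common-gene group, and gives 61% as the detectable alternative. Within TET2 mutants split by a second mutation it claims 80% power for, say, 40% versus 67%.

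Two further statements describe the cohort. Section 1.2.1 sets out to "establish a longitudinal cohort of up to 1750 participants recently diagnosed with MDS and MDS/MPN overlap disorders", while Section 3.1 says that "longitudinal samples and data will be collected for approximately 1000 participants assigned to the longitudinal cohort".

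**The concern.** The HMA sentence in Section 2.1 names the reduced enrolment of about 1750, but its count of treated higher-risk patients fits the original 2000 confirmed cases. Set against the present projection, it asks for as many treated higher-risk patients as there are confirmed MDS patients of any risk.

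Section 2.1 is where the protocol tells investigators what the resource could support. Someone planning a study of HMA response by genotype would take 500 as the expected group, follow the reference to Section 7, find the same 500 there, and read the 61% and the 80% power as attainable.

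**Working it through.** **Inputs.** Confirmed MDS: 2000 originally, 500 now (Section 7.1). Longitudinal participants: about 1000 (Section 3.1). Higher-risk share: 22% + 7% = 29% (Section 2.1). TET2 mutation rate 20%, second-mutation split 50%, response rates 45% v 61% and 40% v 67%, two-sided 5% (Section 7.2.1). The power behind the 61% is not stated; 80% is assumed, as in the neighbouring statement.

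**Counts.**
- Original: 0.29 × 2000 = 580 higher-risk, so up to 500 treated was coherent.
- Current: 0.29 × 500 = 145, if every one is treated.
- If all of the roughly 1000 longitudinal participants had MDS: 0.29 × 1000 = 290.
- Needed to reach 500 at a 29% share: 500 / 0.29 ≈ 1724 confirmed cases, almost the whole enrolment (0.29 × 1750 ≈ 508). The sentence works only if suspected cases are counted as confirmed.

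**Formula.** Two proportions, pooled null variance, with p̄ the weighted mean of p1 and p2:

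power = Φ{ [ |p1 − p2| − 1.96 √( p̄(1 − p̄)(1/n1 + 1/n2) ) ] / √( p1(1 − p1)/n1 + p2(1 − p2)/n2 ) }

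**The plan's own figures, 500 treated.**
- TET2 non-mutant v mutant, 400 v 100, 45% v 61%: p̄ = 0.482; (0.16 − 1.96 × 0.0559) / 0.0548 = 0.92; power 82%. The detectable rate at 80% power is 60.6% (60.4% unpooled, 61.2% continuity-corrected). The stated 61% is reproduced.
- Second-mutation contrast, 50 v 50, 40% v 67%: (0.27 − 1.96 × 0.0998) / 0.0960 = 0.78; power 78% (80% unpooled). The stated 80% is reproduced.

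**At 145 treated.**
- 116 v 29, 45% v 61%: (0.16 − 1.96 × 0.1037) / 0.1017 = −0.43; power 34%. The detectable rate at 80% power is 73% (72 to 75% across the three variants).
- 14 v 15, 40% v 67%: (0.27 − 1.96 × 0.1852) / 0.1786 = −0.52; power 30%. The detectable rate is about 88% (85 to 93%).

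**Sensitivity to the count.**

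| HMA-treated | Basis | Power, 45% v 61% | Detectable v 45% | Power, 40% v 67% |
|---|---|---|---|---|
| 500 | Sections 2.1 and 7.2.1 | 82% | 61% | 78% |
| 290 | all 1000 longitudinal are MDS | 59% | 65% | 54% |
| 145 | 29% of 500, all treated | 34% | 73% | 30% |
| 125 | the original 500 scaled by 500/2000 | 30% | 75% | 26% |

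**Cohort description.** Section 1.2.1 calls up to 1750 people a longitudinal cohort recently diagnosed with MDS or MDS/MPN overlap. Sections 3.1 and 7.1 together give about 1750 enrolled as suspected or newly diagnosed, about 1000 followed longitudinally, and 500 confirmed MDS. Section 1.2.1 treats suspected cases as confirmed ones, as the HMA sentence does.

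**The case against.** The best defence has four parts.

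First, Sections 7.1 and 7.2.1 openly say that the retained calculations rest on the original sample size, and Section 7.1 gives separate figures for 500 cases. This stands. A reader might infer that all the retained power statements are false promises; the documents do not support that, because they are disclosed as historical. The label does not reach Section 2.1, however, which ties the same 500 to the current 1750 in the present tense.

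Second, 145 is not a ceiling. The 29% describes unselected MDS, the protocol gives no risk mix for enrolled cases, and Section 1.2.1 says that most cases tend to worsen, so some patients at lower risk on entry may become higher-risk later. This also stands: 145 is an illustration under a named assumption. It does not rescue 500, which would need all confirmed cases to be higher-risk and treated.

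Third, it is tempting to extend the point to everything in Sections 7.2 and 7.2.1. That goes too far. The quality-of-life example needs 175 people, which 500 cases could still supply if enough meet its haemoglobin and treatment conditions. For ICUS, the protocol projects no current number and Section 3.1 says that the cohort percentages are not known in advance, so no reduced ICUS power can be claimed.

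Fourth, Section 2.1 lists potential studies rather than hypotheses, and any later substudy needs its own approved protocol. This lowers the severity. It does not make the count consistent.

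**Conclusion.** The point holds for the HMA sentence in Section 2.1: as a current expectation, up to 500 treated higher-risk patients cannot be reconciled with 500 confirmed MDS cases of all risk levels. With about 145 treated, the two HMA contrasts fall from about 80% power to 34% and 30%. Even in the generous case of 290 treated they reach only 59% and 54%.

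These figures assume that the unselected-MDS risk mix applies to enrolled cases at entry, that every higher-risk patient receives HMA, and that the 61% was set at 80% power. Section 1.2.1 needs a matching wording correction. No primary analysis, eligibility rule or procedure depends on either passage, so this is a should-fix.

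**What to change.** - **Section 2.1:** replace the 500 with the count implied by 500 confirmed MDS cases (about 145 under the stated risk mix, with that assumption named, or a count from the observed mix if central review now supplies one). Alternatively, label 500 as the original 2000-case assumption.
- **Section 7.2.1, HMA example:** beside the original figures, print the detectable response rate and power at the current count.
- **Section 1.2.1:** describe the cohort as about 1750 enrolled as suspected or newly diagnosed, about 1000 longitudinal and about 500 confirmed MDS, in line with Sections 3.1 and 7.1.
- **Optional:** show the low-risk gene, TP53 and SF3B1 examples at 500 MDS as well. Their present figures are already disclosed as original.

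The cost is a few text edits and a short recalculation. Study conduct does not change; the HMA example simply looks less favourable.
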